2.3 RISK/BENEFIT ASSESSMENT

2.3.1 KNOWN POTENTIAL RISKS

2.3.1.1 Iontophoresis

- May cause mild tingling, prickling and/or warm sensation this is normal and should be anticipated by the participant
- Redness underneath the application site used for iontophoresis
- Dryness or rough skin in area where the iontophoresis was administered
- Skin discoloration or hyperpigmentation

- On rare occasions, iontophoresis therapy can result in transient skin reactions such as rash, inflammation, irritation or burns (blistering). These skin reactions may be the result of:
 - o individual sensitivity to the ionic solution used
 - o the condition of the skin at the onset of treatment
 - o reaction to the materials in the electrodes
 - \circ a poor connection between the electrode and the patient's skin.

Participants will be instructed that if the treatment becomes painful, or if they experience a burning sensation, or an excessive sensation, they should remove the Patch and notify their Treating Therapist.

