6 STUDY INTERVENTION

6.1 STUDY INTERVENTION(S) ADMINISTRATION

6.1.1 STUDY INTERVENTION DESCRIPTION

The study intervention for this project is DSP administered via iontophoresis. Iontophoresis is a noninvasive delivery mechanism for transmitting a medication to a local area of the body. The I-Bresis[™] System and I-Bresis[™] Patch will be the delivery system utilized for this study. The I-Bresis[™] System is indicated for the administration of soluble salts or other drugs into the body for medical purposes as an alternative to hypodermic injection. The I-Bresis[™] System consists of three components: a Charging Station, a rechargeable Controller and a disposable Patch. The I-Bresis[™] Patch is a disposable, single-use patch with a battery and current-limiting circuitry, and can deliver both negatively and positively charged water-soluble drug/compounds across intact skin. The I-Bresis[™] System will be used in accordance with instructions for use.

- Device size(s) Patch: 13.5cm x 6.5cm that holds 1.5mL of fluid on each side of the patch
- Device model(s)
 - I-Bresis[™] charging station: 1360
 - I-Bresis[™] Controller: 1361
 - I-Bresis[™] Patch: 5000060

- Description of each component
 - The I-Bresis[™] charging station is a rectangular piece of equipment that has four charging ports to which I-Bresis[™] Controller attaches. This device is plugged into a standard wall outlet for power. Each individual charging port has a light to signify if the device is charging (yellow) or fully charged (green).²¹
 - The I-Bresis[™] Controller: 1361 is a small triangular device that attaches to the I-Bresis[™] Patch. There are three buttons on top of the device: Power, Start/pause, and standard mode. There is a light on the front of the device that blinks when the device is powered on. The light is solid when the device is running.²²
 - The I-Bresis[™] Patch is a 13.5cm x6.5cm adhesive patch with two "patch drug pads", each of which are labeled with a polarity of either positive (+) or negative (-). Each drug pad holds ~1.5 ml of fluid. Approximately 1.5 ml of a water-soluble drug/solution is placed on one drug pad and approximately 1.5 ml of the saline solution (supplied in the I-Bresis[™] Patch carton as single-use, sealed vials of sterile 0.9% saline solution) is placed on the other.²³
- Device settings and programming : 3mA current for three (3) minutes then 0.67mA for 120 minutes

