- Duration of exposure: 123 minutes (3 minutes of patch + controller, 120 minutes of patch only)
- Frequency of exposure : maximum twice per week for a total of 12 sessions over a maximum of eight (8) weeks

The I-Bresis[™] System is commercially available and will be used in accordance with approved labeling.

The drug and solution administered via the iontophoresis patch will be DSP and 0.9% sodium chloride (placebo).

Dexamethasone sodium phosphate (DSP) is a synthetic adrenocortical steroid that has potent antiinflammatory effects but lacks the sodium-retaining property of hydrocortisone. Corticosteroids inhibit multiple inflammatory cytokines resulting in decreased edema, fibrin deposition, capillary leakage, and migration of inflammatory cells thereby suppressing inflammation. DSP 0.75 mg has anti-inflammatory activity equivalent to approximately 5 mg of prednisone, 25 mg of cortisone, and 20 mg of hydrocortisone. DSP is long-acting (half-life 200 minutes) and is recommended as adjunctive therapy in a variety of inflammatory disorders and as an immunosuppressant agent.¹¹

0.9% Sodium Chloride injection: is a sterile, nonpyrogenic solution of sodium chloride in water for injection. The solution contains 9 grams/L sodium chloride, USP (NaCl), with 154 mEq/L sodium and 154 mEq/L chloride. The nominal pH of sodium chloride is 5.0 (4.5 to 7.0) and osmolarity is 308 mOsmol/L.²⁴

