6.2.4 PREPARATION

DSP and 0.9% sodium chloride will be supplied by the CHKD Pharmacy Department in identical looking bottles, each containing 1.8 mL of solution and labeled in a blinded fashion as either Drug "A" or "B". Trained Therapists will be responsible for the preparation of the iontophoresis patches. Aseptic techniques will be utilized when preparing the patches. Upon randomizing a subject, the treating physical therapist will retrieve the appropriately labeled bottle ("A" or "B", based on the subject's randomization assignment) from the locked cabinet and check the expiration date. The treating physical therapist will apply 1.5 mL liquid (from the assigned bottle) to the negative side of the patch per the instructions listed in the I-Bresis Instruction for Use. The Therapist will then apply 1.5mL of 0.9% sodium chloride from the saline ampoules provided in the I-Bresis[™] carton to the positive side of the patch and will then obtain two patient identifiers (ex. Full name, DOB) from the patient prior to patch application per clinic policy.

The treatment site will be cleaned thoroughly with alcohol prep (ensuring the area being treated is free from other creams and topical medications, including topical steroids) as described in the instructions listed in the I-Bresis Instructions for Use.²³ The negative side of the patch will be applied over the tibial tubercle in patients with OSD and over the inferior patellar pole in patients with SLJ.

The I-Bresis controller will be turned on then connected to the patch. At that time, the start button will be pressed and the current will be initiated at 3mA for an initial 3minutes of treatment. Following this three minutes, the controller will be removed and turned off. The Patch will remain in place and an 80 mA-minute dose will be applied over two hours. The therapist will ensure that the patch fully conforms to the patient and that it will maintain full contact with the skin. To improve adhesion of the patch, the therapist may lightly wrap the patch with Pre-Wrap and secure the end with tape, ensuring the tape is not being applied over the patch so as not to bind it.

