Subjects will be monitored by their therapist for adverse events for 15 minutes after the patch is applied following the initial application and for an appropriate amount of time following all subsequent applications. Subjects will leave the PT clinic with the patch in place. The patch will be programed to deliver medication over a two-hour period, automatically switching off iontophoresis after the maximum dose has been administered. Subjects will be instructed to remove the patch 2 hours after it has been applied as leaving the patch on longer than the recommended time may increase the risk of skin irritation. Subjects will be instructed to wrap the patch in paper towels and discard the Patch in a receptacle out of reach of children and pets.

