8.2 SAFETY AND OTHER ASSESSMENTS

The following procedures/evaluations will be obtained by qualified Therapists treating the subjects: Assessed At Enrollment/Randomization Study Treatment Visit 1:

 Inclusion/Exclusion Criteria - Based on the patient's medical history and review of the initial evaluation, the Treating Therapists will determine whether patients meet eligibility criteria for the study.

Note: if radiograph images were obtained to determine skeletal maturity, the Treating Therapist will ensure the results are documented in the radiologist's notes or noted in the physician's notes in the electronic medical record.

- Informed Consent Treating Therapist will conduct the informed consent process as outlined in Section 10.1.1.2 of this document.
- Randomization After a patient signs Consent, the Treating Therapist will assign the patient to the research group per the randomization log at the Site (see section 6.3 Measures to Minimize Bias: Randomization and Blinding).

Assessed at All Study Treatment Visits:

- Brief Physical examination of the affected knee an evaluation made by the treating physical therapist to include: skin color, temperature, presence of edema, turgor, pain with palpation/pressure, changes to skin texture, and integrity. Also assessed at Clinic Check visit.
- Concomitant Medication Review a paper-based form completed by the Treating Therapist to document drug, dose, frequency, start and stop dates, and reason for taking. Also assessed at Clinic Visit Check visit.
- Adverse Event Evaluation a paper-based form completed by the Treating Therapist to document occurrence, severity, relatedness, duration, and expectedness of the event. Subjects receiving iontophoresis will be specifically monitored for possible burns. This data will be captured during the examination of the affected knee as well as for 15 minutes post patch application.

Also assessed at Clinic Visit Check visit, 30-Day Phone Follow Up and electronically at the 90-Day Follow Up (see Appendix 12.6 90-Day Follow Up – Electronic Survey)

• Compliance Checks – a paper-based form completed by the Treating Therapist to assess participant compliance with: study visits, length of time iontophoresis patch worn, home exercise program, icing, activity restriction, and bracing instructions. Also assessed at Clinic Check visit.

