8.3.4 TIME PERIOD AND FREQUENCY FOR EVENT ASSESSMENT AND FOLLOW-UP

The occurrence of an AE or serious adverse event (SAE) may come to the attention of study personnel during study visits, during the 30-day follow up phone call or from the 90-day electronic survey. AEs will be assessed at each treatment visit through the performance of a brief physical exam, interview by the Treating Therapist, review of concomitant medications, as well as from patient-reported responses to the FACES Pain scale and LEFS (assessed only at Study Treatment Visit 1, 5, 12, and 30-day follow-up).

All AEs including local and systemic reactions not meeting the criteria for SAEs will be captured on the appropriate case report form (CRF). Information to be collected includes event description, time of onset, clinician's assessment of severity, relationship to study product (assessed only by those with the training and authority to make a clinical assessment), expectedness, and time of resolution/stabilization of the event. All AEs occurring while on study will be documented appropriately regardless of relationship. All AEs will be followed to adequate resolution or stabilization.

Any medical condition that is present at the time that the participant is screened will be considered as baseline and not reported as an AE. However, if the study participant's condition deteriorates at any time during the study, it will be recorded as an AE.

Changes in the severity of an AE will be documented to allow an assessment of the duration of the event at each level of severity to be performed. AEs characterized as intermittent require documentation of onset and duration of each episode.

The treating Therapist will record all reportable events with start dates occurring any time after informed consent is obtained until 90 days after RTS criteria met or participant has received study treatment for eight (8) weeks, whichever is the shorter of the two time periods. At each study visit, the treating Therapist will inquire about the occurrence of AE/SAEs since the last visit. Events will be followed for outcome information until resolved or deemed by PI and Independent Safety Monitor as chronic or stable.

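### Brief skin reactions after the patch comes off at home reach the safety endpoint only through general report, so mild, painless ones can be under-counted

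*Combined protocol and SAP*

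**What the plan says.** - **Burn capture.** Section 8.2, under the assessments made at all study treatment visits, says patients on iontophoresis are watched specifically for burns, and names two capture points: "This data will be captured during the examination of the affected knee as well as for 15 minutes post patch application".
- **Observation time.** Section 6.2.4 sets the monitoring time differently: "for 15 minutes after the patch is applied following the initial application and for an appropriate amount of time following all subsequent applications".
- **Patch status.** Section 6.2.4: "Subjects will leave the PT clinic with the patch in place". The subject takes it off two hours after application; Section 8.1 places those two hours at home.
- **Current.** Section 6.1.1: "3mA current for three (3) minutes then 0.67mA for 120 minutes". Section 6.2.4: "The Patch will remain in place and an 80 mA-minute dose will be applied over two hours".
- **Visit spacing.** Section 6.1.1 allows at most two sessions a week and 12 sessions within eight weeks. Section 8.1 puts the Clinic Check two to three business days after return-to-sport (RTS) clearance or eight weeks of treatment.
- **Skin examination.** The brief knee examination in Section 8.2 covers skin color, texture and integrity, at every treatment visit and the Clinic Check.
- **Other capture routes.** Section 8.3.4: "At each study visit, the treating Therapist will inquire about the occurrence of AE/SAEs since the last visit". Section 2.3.1.1 tells participants to take the patch off and tell the therapist if treatment is painful, burning or excessive in sensation.
- **Role of these events.** Section 2.3.1.1 describes rash, irritation and burns with blistering as rare and transient. Section 2.3.3 ranks local skin reactions among the side effects of most concern. The safety endpoint is the number and intensity of related adverse events.

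**The concern.** The check after application takes place while the patch covers the treated skin and before most of the current has passed. When the skin is uncovered, no study staff are present, and the protocol text schedules no record of what it looked like. The next look is days later, for reactions that the plan itself expects to be short-lived.

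A reaction that appears on removal and clears before the next visit therefore depends on what the child or parent says. The instruction in Section 2.3.1.1 is triggered by sensation, so painless redness or discoloration does not set it off. The inquiry in Section 8.3.4 is general. The nearest wording the documents supply, for the 30-day call in Appendix 12.5, asks about doctor visits and new medical problems, which a family may not connect with a day of redness.

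Intensity is affected as well as number. Section 8.3.4 asks for onset, severity and duration at each severity level, and Section 8.3.3.2 gives the causality judgment to the therapist who examined the participant. For a reaction that has cleared, those entries would rest on non-specific recall of something the therapist did not see.

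**Working it through.** **1. Reproduce the plan's figure.** Charge = current × time. Patch phase: 0.67 mA × 120 min = 80.4 mA-min, against 80 stated in Section 6.2.4 (difference 0.4/80 = 0.5%). It reproduces.

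**2. Total per application.** Controller phase: 3 mA × 3 min = 9 mA-min. Total: 9 + 80.4 = 89.4 mA-min over 123 minutes.

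**3. Charge delivered when a 15-minute check ends.** The documents do not say when the clock starts, or whether the 9 mA-min is inside the 80, so all readings are shown.

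| Reading | Delivered | Total | Delivered | Still to come |
|---|---|---|---|---|
| From start of current | 9 + 0.67 × 12 = 17.04 | 89.4 | 19.1% | 80.9% |
| From controller removal | 9 + 0.67 × 15 = 19.05 | 89.4 | 21.3% | 78.7% |
| 9 counted inside 80, from start | 9 + (71/120) × 12 = 16.1 | 80 | 20.1% | 79.9% |
| 9 counted inside 80, from removal | 9 + (71/120) × 15 = 17.9 | 80 | 22.3% | 77.7% |
| Patch phase only | 0.67 × 15 = 10.05 | 80.4 | 12.5% | 87.5% |

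Under every reading 78% to 88% is still to come. In time, the check covers 15/123 = 12% to 18/123 = 15% of the exposure.

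**4. Gap to the next skin examination.** At two visits a week: 7/2 = 3.5 days on average. If 12 sessions fill eight weeks: 56/12 = 4.7 to 56/11 = 5.1 days. After RTS clearance: 2 to 3 business days.

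**5. Chance that a reaction is still visible at the examination (assumption).** The documents give no duration for a reaction. With exponentially distributed durations, the chance is exp(−gap/mean).

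| Mean duration (days) | Gap 2 days | Gap 3.5 days | Gap 5 days |
|---|---|---|---|
| 0.5 | 2% | 0.1% | <0.1% |
| 1 | 14% | 3% | 1% |
| 3 | 51% | 31% | 19% |
| 7 | 75% | 61% | 49% |

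This is detection by examination alone. Detection by interview cannot be quantified from the documents.

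**6. Effect on the A versus B comparison (assumption).** Section 9.2 gives 108 participants for the safety hypothesis without event rates, so power lost cannot be derived from it. As an illustration, take n = 49 per arm and true rates of 30% and 10%, both multiplied by the same capture fraction c. The normal-approximation power, two-sided 0.05, is Φ{[|p1 − p2| − 1.96√(2p̄(1 − p̄)/n)] / √([p1(1 − p1) + p2(1 − p2)]/n)}.

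| Capture c | Observed rates | Power |
|---|---|---|
| 1 | 30% v 10% | 0.70 |
| 0.75 | 22.5% v 7.5% | 0.55 |
| 0.5 | 15% v 5% | 0.38 |

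The ratio of rates stays at 3 in every row; the difference and the power fall.

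**7. Sections 8.2 and 6.2.4 side by side.** Section 8.2 lists the 15 minutes under all treatment visits. Section 6.2.4 fixes 15 minutes for the initial application and leaves later ones open. On the text of Section 6.2.4, up to 11 of 12 applications have no fixed time, and the percentages in step 3 cannot be computed for them.

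**The case against.** The strongest case is that the plan does not rely on the two examinations alone. The therapist asks about adverse events at every visit, participants are told to notify the therapist of pain or burning, and the adverse event form records occurrence, severity and duration. Interview plus skin examination at each treatment visit is an accepted method. This stands, and it rules out several stronger readings:

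- A reader might infer that a reaction gone by the next visit is lost, or depends on unprompted recall. Section 8.3.4 provides a prompt, though a general one.
- A reader might take the percentages in step 5 as the share of reactions captured. They rest on assumed durations and leave out the interview. Blistering or discoloration that lasts would probably still be seen.
- A reader might infer bias toward DSP or placebo. Groups A and B share one schedule, and their participants and therapists are blinded, so equal under-capture does not favour an arm.
- A reader might count 98 × 12 = 1,176 affected applications. That is a ceiling on patches applied, not a count of missed events: treatment stops at RTS, and the plan calls burns and rashes rare.
- A reader might conclude that nobody asks about the skin at removal. The compliance and adverse event worksheets are not reproduced in the appendices. One can say only that the protocol text specifies no such question.

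What the objection does not answer is the brief, painless reaction noticed at removal. The notify instruction does not cover it, and no described question is aimed at it.

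**Conclusion.** The point holds in a limited form. Brief reactions after removal at home are not seen by the therapist under the protocol's schedule. They are captured only by general inquiry or by a sensation-triggered notification. Mild, painless ones can be under-counted, and their intensity and duration graded from non-specific recall.

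The timing is firm: roughly 80% of the charge follows a 15-minute check (78% to 88% across readings), and the next scheduled skin examination is about 3.5 to 5 days away during treatment, or 2 to 3 business days after RTS clearance.

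The size of the under-count is not known and cannot be derived from the documents. Its direction is toward lower absolute rates in both patch groups and less power for DSP versus placebo, given equal capture in A and B. The power figures above illustrate this under assumed rates only. The point supports a cheap improvement to data capture; it does not show that the safety assessment fails.

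**What to change.** 1. For Groups A and B, add fixed questions to the compliance form, next to patch wear time: when the patch came off, was there redness, blistering or broken skin, or discoloration; how long did it last; was the patch removed early because of it. If the worksheets already hold such questions, state them in Section 8.2.
2. Ask the same questions at the first study contact after the last patch.
3. In Section 9.4.4, report the answers as solicited events by arm (A versus B), separately from other adverse events.
4. Reconcile Sections 8.2 and 6.2.4 on which applications the 15 minutes covers.

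Items 1 to 3 change no observation time or patch handling. The cost is two or three form lines per visit and one extra safety table, with no added staff or procedure. The downside is that prompting will raise the count of mild reactions, which is why they need a table of their own. The answers remain recall, but of a specific moment and specific signs.

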8.3 ADVERSE EVENTS AND SERIOUS ADVERSE EVENTS

8.3.1 DEFINITION OF ADVERSE EVENTS AND SUSPECTED ADVERSE REACTION

Adverse event (AE) means any untoward medical occurrence associated with the use of an intervention in humans, whether or not considered intervention-related (21 CFR 312.32 (a)).

Suspected adverse reaction means any adverse event for which there is a reasonable possibility that the drug caused the AE. For the purposes of IND safety reporting, "reasonable possibility" means there is evidence to suggest a causal relationship between the drug and the AE.

8.3.2 DEFINITION OF SERIOUS ADVERSE EVENTS (SAE) OR SERIOUS SUSPECTED ADVERSE REACTION

An AE or suspected adverse reaction is considered "serious" if, in the view of the investigator or Sponsor, it results in any of the following outcomes: death, a life-threatening adverse event, inpatient hospitalization or prolongation of existing hospitalization, a persistent or significant incapacity or substantial disruption of the ability to conduct normal life functions, or a congenital anomaly/birth defect. Important medical events that may not result in death, be life-threatening, or require hospitalization may be considered serious when, based upon appropriate medical judgment, they may jeopardize the participant and may require medical or surgical intervention to prevent one of the outcomes listed in this definition.

8.3.3 CLASSIFICATION OF AN ADVERSE EVENT

8.3.3.1 SEVERITY OF EVENT

The Treating Therapists trained on this protocol will be responsible for classifying an AE. All AEs will be assessed for severity using the definitions below:

- Severity of Event (Intensity) The following guidelines will be used to describe severity:
 - **Mild** Events require minimal or no treatment and do not interfere with the participant's daily activities.
 - Moderate Events result in a low level of inconvenience or concern with the therapeutic measures. Moderate events may cause some interference with functioning.
 - Severe Events interrupt a participant's usual daily activity and may require systemic drug therapy or other treatment. Severe events are usually potentially life-threatening or incapacitating.

